## Protocol Overview

|  |   |
|--|---|
| Protocol Title:  | Thyroid hormone to induce non-insulin mediated glucose disposal in patients with insulin receptor mutations |
| Abbreviated Title:   | T3 in insulin receptor mutations  |
| IRB:   | NIDDK/NIAMS   |
| Research Type:   | Phase II Clinical Trial   |
| Multi-site Collaboration:  | No  |
| Intramural Collaboration:  | No  |
| Ionizing Radiation Use:
(X-rays, e.g., CT; radioisotope, e.g. PET;
etc.) | Research Indicated  |
| Investigational New Drug/Device:   | No  |
| Patient Self-Referral Allowed:   | Yes   |
| List Protocol On Web:  | Yes   |
| Is tissue being collected for research purposes:                               | Yes   |

## Conflict of Interest

|  |
|--|
| The protocol involves no drugs/devices/products that may lead to payments and/or royalties to be paid to the investigators or the NIH.   |
| The investigators have no equity, consultative, or other financial relationship with a non-NIH source related to this protocol which might be considered a conflict of interest. |

## Time Frame

|             |            |
|-------------|------------|
| Start Date: | 12/1/2014  |
| End Date:   | 11/30/2020 |

## Precis – Abstract

### *Background*

Patients with mutations of the insulin receptor have extreme insulin resistance. This frequently results in diabetes in childhood that is extremely difficult to manage with conventional diabetes therapies, including insulin at doses 10-50 fold higher than usual. Poorly controlled diabetes, in turn, leads to microvascular complications (e.g. blindness) and early death. Hyperthyroidism, whether endogenous (e.g. Graves' disease) or exogenous, increases energy expenditure, activates brown adipose tissue, and enhances skeletal muscle perfusion, leading to enhanced glucose disposal. In a single patient with mutation of the insulin receptor and poorly controlled diabetes despite maximal therapy, iatrogenic mild hyperthyroidism for treatment of thyroid cancer resulted in normalization of glycemia control, suggesting that thyroid hormone treatment could have therapeutic benefit in this rare disease.

### *Aim*

The purpose of this study is to determine if treatment with thyroid hormone will increase glucose disposal in patients with mutations of the insulin receptor, and thereby improve glycemia control. The hypotheses to be tested are:

- Thyroid hormone will increase whole-body glucose disposal in patients with insulin receptor mutations.
- This increased glucose disposal will be mediated via increased glucose uptake in BAT and muscle.
- Increases in glucose disposal will result in improved glycemia control.

### *Methods*

This study is a non-randomized pre-post design, conducted in two sequential parts. Part 1 is a short-term (2 week) proof-of-principle study to test whether thyroid hormone will increase glucose disposal in patients with insulin receptor mutations (with or without diabetes), and the mechanisms by which increased glucose disposal occurs. Part 2 is a longer term (6 month) therapeutic study to test whether thyroid hormone will result in improved glycemia control in diabetic patients with insulin receptor mutations.

## Study Objectives

Part 1 (2 week study): The primary aim of this study is to determine if triiodothyronine (T3) treatment will increase glucose disposal in patients with mutations of the insulin receptor. The null hypothesis is that T3 will have no effect on glucose disposal. The alternative hypothesis is that T3 will increase glucose disposal.

Part 2 (6 month study): The primary aim of this study is to determine if triiodothyronine (T3) treatment will improve diabetes control, measured as hemoglobin A1c, in patients with mutations of the insulin receptor. The null hypothesis is that T3 will have no effect on A1c. The alternative hypothesis is that T3 will decrease A1c.

## Introduction

### *Insulin receptor mutations*

Mutations of the insulin receptor result in extreme insulin resistance and dysglycemia in humans. These disorders have a spectrum of clinical severity linked to the degree of residual activity of the insulin receptor. Three clinical syndromes have been described: infants with Donohue syndrome (also called leprechaunism) and children with Rabson-Mendenhall syndrome (RMS) have characteristic dysmorphic features, and frequently have fasting hypoglycemia coupled with postprandial hyperglycemia, while patients classified as Type A insulin resistance lack dysmorphisms. The majority of patients who survive beyond two years of age (RMS and Type A insulin resistance) develop persistent hyperglycemia as endogenous insulin secretion declines. Hyperglycemia in patients with insulin receptor mutations is extremely difficult to treat, and patients are at risk for early morbidity and mortality from microvascular complications of diabetes.

High doses of concentrated insulin have been used to treat patients with insulin receptor mutations in an effort to maximize any residual insulin receptor signaling. Recombinant insulin-like growth factor-1 (IGF-1) has also been tried in small numbers of patients, and appears to be most effective in those with the mildest form of the disease. In our experience, IGF-1 has not been useful in the most severely affected patients, and if its action is through residual insulin receptor activity, it is more logical and safer to use high-dose insulin. Other conventional glucose lowering therapies, such as metformin, may be modestly beneficial in patients with insulin receptor mutations, but additional glucose lowering treatments that do not require signaling through the insulin receptor are required for effective treatment of these conditions.

### *Brown adipose tissue*

Brown adipose tissue (BAT) has recently gained attention as a potential target to increase energy expenditure in adult humans. Whereas white adipose tissue (WAT) functions primarily as an energy storage organ, BAT burns energy for thermogenesis. It does this through the action of uncoupling protein-1 (UCP-1), which allows leakage across the mitochondrial electrochemical gradient, causing the energy generated from substrate oxidation to be released as heat rather than used to form ATP. Major activators of BAT include cold, beta-adrenergic receptor (primarily  $\beta_3$ ) stimulation, and thyroid hormone. Although the primary substrate utilized by BAT is free fatty acids, BAT also takes up glucose, and BAT activation has the potential to increase glucose utilization in diabetic individuals.

The role of thyroid hormone excess in glucose metabolism has been investigated in several studies in humans with normal insulin receptor function. In general, patients with hyperthyroidism have *increased* blood glucose in the fasting and post-prandial states. This worsening of glucose metabolism appears to be due to worsening of post-receptor insulin resistance, particularly at the level of the liver, resulting in increased hepatic glucose production. In contrast, hyperthyroid patients (compared to euthyroid controls) have a 3-fold increase in glucose uptake in BAT, and 1.9-fold increase in glucose uptake in muscle; these normalize once patients return to a euthyroid state.

Recently, Lahesmaa et. al., reported that BAT takes up  $2.7 \pm 2.3$   $\mu\text{mol}/100\text{g}/\text{min}$  of glucose in the hyperthyroid state, and takes up  $0.9 \pm 0.1$   $\mu\text{mol}/100\text{g}/\text{min}$  of glucose in the euthyroid state. They also showed that in the hyperthyroid state, skeletal muscle takes up  $1.9 \pm 0.6$   $\mu\text{mol}/100\text{g}/\text{min}$  of glucose, and in the euthyroid state, takes up  $1.0 \pm 0.3$   $\mu\text{mol}/100\text{g}/\text{min}$  of glucose. If we assume that an average human possesses  $\sim 50\text{g}$  of BAT, and  $\sim 30,000\text{g}$  of muscle, then BAT will take up an excess of  $0.9$   $\mu\text{mol}/\text{minute}$  of glucose in the hyperthyroid vs. the euthyroid state, and muscle will take up an excess of  $270$   $\mu\text{mol}/\text{minute}$  of glucose in the hyperthyroid vs. the euthyroid state. Thus, muscle is anticipated to be the major organ taking up excess glucose in the presence of T3 treatment.

Taken together, these data suggest that, in patients with fixed insulin resistance due to insulin receptor mutations, thyroid hormone might enhance glucose disposal without worsening insulin resistance, resulting in a net improvement in glucose homeostasis.

## Subject Eligibility Assessment and Enrollment

### 2 week study:

#### *Inclusion Criteria*

- Mutation of the insulin receptor (either recessive or dominant negative). If mutation status is not known prior to enrollment, subjects will undergo genotyping at enrollment. In the unanticipated event that a patient does not have a mutation of the insulin receptor, he or she will not complete the study and his or her data will not be included in the analysis.
- Age 12 to 65 years old

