## **Study Implementation**

Subjects will be admitted to the Metabolic Research Unit in the NIH Clinical Center. They will remain as inpatients throughout the 19 day duration of the short-term study. Upon admission, they will undergo a history and physical examination, and baseline labs will be obtained. Labs used to assess subject eligibility in all subjects include electrolytes, BUN, creatinine, CBC, and a pregnancy test for female patients of reproductive potential. Baseline serum 25-hydroxyvitamin D levels will be obtained in all subjects. In subjects with 25-hydroxyvitamin D levels below 20 ng/mL, vitamin D supplementation will be provided. An EKG and echocardiogram will be performed to assess eligibility. Height, weight, blood pressure, resting pulse, temperature will be obtained.

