#### ***Liothyronine (T3)***

T3 is the active form of thyroid hormone. Our rationale for choosing liothyronine (T3) over levothyroxine (T4) for this study is for two reasons. First, due to the short duration of the initial proof of principle study (two weeks), we would prefer to use a formulation of thyroid hormone with a short half-life that can be rapidly titrated. The half-life of liothyronine is a few hours, versus levothyroxine which is one week, thus allowing us to rapidly titrate the dose. Secondly, we prefer to use a formulation of thyroid hormone that will maximally stimulate BAT without the need for conversion from T4 to T3 by type 2 deiodinase. By using liothyronine as opposed to levothyroxine, we are able to study the direct effect of T3 on BAT, and are essentially eliminating an additional step.

Replacement doses of T3 to achieve euthyroidism in hypothyroid adults are approximately 0.57 mcg/kg/day. Stable plasma T3 levels can be achieved with q8 hour T3 dosing. In this study, the goal will be to achieve peak plasma T3 levels between 125% and 150% of the upper limit of normal (200 ng/dL in the NIH Clinical Center laboratory). The estimated T3 dose to achieve this level of plasma T3 is 2 times the replacement dose, or 1.14 mcg/kg/day. In a 50 kg individual, this equals 57 mcg. T3 is available in dosing increments of 5 mcg; thus doses will be rounded (lower dose will be used if calculated dose is 0 to <2.5 mcg above a dose divisible by 5; higher dose will be used if dose is 2.5 to <5 mcg above a dose divisible by 5). By comparison, T3 at doses of 150 mcg per day (~2.1 mcg/kg/day, or

approximately 4 times the replacement dose) was given to healthy, euthyroid adults for 2 weeks, raising plasma T3 levels from 125 to 507 ng/dL. This treatment was well tolerated, with an increase in heart rate from 65 to 78 beats per minute, and weight loss of 2 kg, and the development of “mild to moderate symptoms of enhanced appetite, nervousness, headache, or palpitations”. In a similar study, T3 at doses of 75 to 100 mcg per day (1.1 to 1.4 mcg/kg/day) was given to healthy, euthyroid adults for 2 weeks, raising plasma T3 levels from 110 to 350 (range, 190-520) ng/dL, with no reported adverse events.

The dose titration scheme for T3 is as follows:

- Day 1: 1x replacement (0.57 mcg/kg/day)
- Day 2: 1.5x replacement (0.855 mcg/kg/day)
- Days 3-14: 2x replacement (1.14 mcg/kg/day)

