### **Rationale for Subject Selection**

Subjects eligible for this study include adults and children who are 12 years or older with mutations of the insulin receptor. Children less than 12 years of age will be excluded because they are unlikely to possess the emotional maturity needed to undergo the intense testing regimen, and because young children with insulin receptor mutations are less likely to have overt diabetes or complications of diabetes. Adolescents age 12-17 will be included because overt diabetes (and its complications) commonly develops during puberty in this patient population, and they are likely to be able to comply with study procedures. Because each subject will be compared to him/herself in this within-subjects design, the effects of inter-subject heterogeneity will be less important.

For adult participants, the short-term component of this study is of greater than minimal risk, and has no prospect of direct benefit. For adult participants, the long-term component of this study is of greater than minimal risk, and with prospect of direct benefit to subjects. For minor participants, the short-term component of this study involves a minor increase over minimal risk and has no prospect of direct benefit, but is likely to yield generalizable knowledge about the subjects' disorder or condition. For minor participants, the long-term component of this study is of greater than minimal risk, and with prospect of direct benefit to subjects.

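### Subjects can enrol before their insulin receptor mutation is confirmed, and nothing makes the baseline research procedures or the first T3 dose wait for the genotype result

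*Combined protocol and SAP*

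**What the plan says.** An insulin receptor mutation is the only disease criterion for the 2 week study. The Inclusion Criteria allow for subjects in whom it has not been shown: "If mutation status is not known prior to enrollment, subjects will undergo genotyping at enrollment". If the test is negative, which the protocol does not anticipate, "he or she will not complete the study and his or her data will not be included in the analysis". The age criterion is "Age 12 to 65 years old", so this applies to minors as well as adults.

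Study Implementation says of the subjects: "They will remain as inpatients throughout the 19 day duration of the short-term study". The short-term schedule under Study Procedures has four off-T3 days (0 to 3) followed by on-T3 days 1 to 15. The Liothyronine (T3) section starts titration on day 1 and sets no condition about genotype.

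The 6 month study requires the same entry criteria plus poorly controlled diabetes, so it carries the same exception. Under Sample Size Justification, eligible and consenting subjects move into it without a break. Withdrawal Criteria list breach of an entry criterion, which takes effect only once a subject is in the study.

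**The concern.** The rule enrols first and removes later. Dropping a mutation-negative subject's data protects the analysis. It does not protect the person, who may already have had research procedures and study drug.

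The protocol's own argument for T3 does not reach that person. On thyroid hormone excess in people with normal insulin receptor function, the Introduction says: "This worsening of glucose metabolism appears to be due to worsening of post-receptor insulin resistance". It then argues for a net gain in glucose homeostasis only where resistance is fixed by a receptor mutation.

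For minors there is a second difficulty. Rationale for Subject Selection states that their short-term component "involves a minor increase over minimal risk and has no prospect of direct benefit", and supports it by the knowledge it should yield about the condition they have. A minor without a mutation does not have that condition, and the inclusion criterion removes that minor's data from the analysis.

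**Working it through.** **1. Does any section hold exposure until the result is known?**

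| Section | What it contributes |
|---|---|
| Inclusion Criteria, 2 week study | Genotyping at enrolment; a negative subject is stopped; no timing relative to procedures or T3 |
| 6 month study criteria | Repeats the 2 week criteria, including the exception |
| Sample Size Justification | Immediate move to the 6 month study; no genotype check |
| Study Implementation | "Labs used to assess subject eligibility in all subjects include electrolytes, BUN, creatinine, CBC, and a pregnancy test"; genotype not named |
| Liothyronine (T3) | Titration starts on day 1; no genotype condition |
| Study Procedures, short-term schedule | No genotyping row |
| Withdrawal Criteria | Entry violation handled after entry |

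None supplies the link. The laboratory list and the missing schedule row are weak evidence, because the list covers tests done in everyone and genotyping is needed only for subjects of unknown status. What matters is that no section states the condition.

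**2. Timing.** Call admission day 0. Off-T3 days 0 to 3 are days 0 to 3, and on-T3 day *k* is day 3 + *k*. The total is 4 + 15 = 19 days, which agrees with the stated stay. The first T3 dose falls on day 4. The schedule places the tracer study on day 1, and the PET-CT and both biopsies on day 3.

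**3. T3 exposure before a result.** Assume the sample is taken on admission and the result arrives on day *t*. On-T3 days begun by then = max(0, min(*t* − 3, 15)). The values of *t* are assumptions, because the documents give no turnaround.

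| Result on day *t* | On-T3 days begun |
|---|---|
| 3 or earlier | 0 |
| 7 | 7 − 3 = 4 |
| 14 | 14 − 3 = 11 |
| 21 | min(18, 15) = 15 (14 if counted by the titration scheme, which lists doses for days 1 to 14) |

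**4. Baseline exposure.** A mutation-negative subject of any age could have the tracer study, which includes albumin-complexed palmitate. An adult could also have one PET-CT and, unless he or she opts out, adipose and muscle biopsies. The radiation figures give 1.22 rem for two PET scans and three DEXA scans at 0.00003 rem each: (1.22 − 0.00009) / 2 ≈ 0.61 rem per PET-CT. Minors have neither PET-CT nor biopsies.

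**5. Is power affected?** Power is P(|T| > t(0.975, n − 1)), where T is noncentral t with n − 1 degrees of freedom and noncentrality (0.39 / 0.27)√n. The plan gives the SD only as below 0.27, so 0.27 is used. At n = 6 the noncentrality is 1.444 × 2.449 = 3.54 and power is 80.5%; at n = 5 it is 68.0%. This reproduces the plan's 6. With 10 analysed subjects power is 98.1%, with 9 it is 96.5% and with 8 it is 93.6%. Losing one or two mutation-negative subjects from the target of 10 leaves power well above 80% on the plan's own inputs.

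**The case against.** The strongest reply is that the harm is inferred from silence. No section says T3 will start with a genotype pending. A subject without a mutation fails an inclusion criterion. The protocol confirms other criteria after admission too: laboratory tests, EKG and echocardiogram are done then. Consent must come before any study procedure, so a protocol genotype can only be drawn after consent. Genotyping at enrolment could therefore be meant as a screening step, and the removal clause as a screen failure.

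That reading is possible and cannot be ruled out. It is not written down, however, and a site following the text could proceed either way. The gap stands as something the plan permits, not something it intends.

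Three stronger inferences are tempting, and the documents do not support them:

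- *The protocol expects glycemia to worsen in mutation-negative subjects.* The Introduction describes hyperthyroid patients in general. It makes no prediction for a mutation-negative referral on two weeks of monitored T3, and it also reports higher brown fat and muscle glucose uptake in hyperthyroidism.
- *The stated risk category fails for adults.* Their category is not worded by genotype, and the T3 section describes two weeks of higher-dose T3 in healthy adults as well tolerated. Only the rationale gap applies to adults.
- *All information from such a subject is lost.* The exclusion concerns the analysis. The adverse event section has all adverse events recorded and submitted.

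It also stands that numbers are likely small. The protocol regards a negative result as unanticipated, and 17 patients with mutations are already followed, against a target of at least 10 and a cap of 20. Referrals from physicians elsewhere remain a possible source of subjects with unknown status.

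**Conclusion.** The concern holds as a gap in eligibility timing. The plan allows enrolment before the defining criterion is confirmed, and no section requires the result before the baseline research procedures or before T3 on the fourth day after admission.

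The size depends on an unstated turnaround. T3 exposure could be none or the full 2 week course, preceded by the tracer study and, in adults, about 0.61 rem from one PET-CT and optional biopsies. The case is firmest for minors, because the justification for their no-benefit participation rests on having the disorder. For adults it is a mismatch with the scientific rationale and no more.

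This is a matter of subject protection. Few people are likely to be affected, and neither power nor the primary estimate is at stake. A reader should not conclude that the trial plans to treat people without a mutation; it only fails to prevent it.

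**What to change.** Amend the inclusion criterion so that, for a subject of unknown status, the genotyping sample is taken after consent and a positive result is on file before any baseline research procedure and before the first T3 dose. Mark the same requirement in the short-term schedule.

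Keep the removal clause as a fallback. It is the only explicit rule for a subject later found negative, and deleting it would leave that case uncovered. Add that adverse events in any exposed mutation-negative subject are still reported under the adverse event section, although the subject is left out of the analysis.

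The test is already planned, so no new assay is needed. The cost is a delay equal to the genotyping turnaround for the few subjects of unknown status and, for distant referrals, possibly a separate sample before travel. Because entry also requires 10 weeks without a change in diabetes medication dose, waiting may lengthen that stable period for them.

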#### *Exclusion Criteria*

- Changes in doses of diabetes medications (including metformin, insulin, sulfonylureas, thiazolidinediones, leptin, GLP-1 agonists, DPP4 inhibitors, etc.) in the preceding 10 weeks.
- Any medical condition or medication that will increase risk to the subject (e.g. ischemic or structural heart disease, congestive heart failure, uncontrolled hypertension, or arrhythmia) or that will interfere with interpretation of study data.
- Disorders that would lead to erratic gastrointestinal absorption or loss of thyroid hormone from the gut (severe diarrhea, celiac disease, use of bile acid sequestrants, excessive consumption of soybean products).
- Any form of endogenous hyperthyroidism or hypothyroidism at baseline.
- Current or recent (past 8 weeks) use of thyroid hormone or anti-thyroid drugs.

- Extreme disorders of thyroid hormone binding to thyroid binding globulin (excess or deficiency) or protein loss (nephrotic range proteinuria) that would lead to difficulties achieving a consistent thyroid hormone level for study.
- Known presence of a rare clinical disorder that leads to thyroid hormone insensitivity (known T3 receptor mutations, selenocysteine insertion sequence-binding protein 2 (SBP2) abnormalities, monocarboxylate transporter defects).
- Current use of beta blockers
- Pregnancy or breast feeding
- Any EKG abnormality that could increase risk of T3 treatment (resting sinus tachycardia (age adjusted norms), atrial fibrillation, myocardial ischemia, left or right ventricular excitation block, left ventricular hypertrophy or extrasystoles)
- Known allergy or hypersensitivity to any form of thyroid hormone
- Known adrenal insufficiency
- Dependence on oral anticoagulant medications (adults only)
- Use of tricyclic anti-depressants, as transient cardiac arrhythmias have been observed with the concomitant use of thyroid hormone.
- Use of cholestyramine.
- History of clinically significant osteoporosis per investigator judgment (e.g. previous fragility fracture)

